4 RESEARCH QUESTION/AIM(S)

4.1 Primary aim:

To determine whether blood biomarkers sensitive to neuronal injury are elevated in the sub-acute to chronic period following confirmed environmental, non-fire related exposure to CO.

4.2 Secondary aims:

- Establish whether the prevalence of neurological, cognitive and behavioural deficits associated with CO exposure can be estimated;
- Develop a sensitive and specific neurocognitive testing battery for CO poisoning

Cognitive and blood biomarker assessment after CO Exposure

- Characterize the neurological, cognitive and behavioural impairments following a confirmed CO poisoning event

4.3 Outcomes:

Blood biomarker levels in patients with proven CO exposure.

Cognitive and behavioural profiles of patients with proven CO exposure

5 STUDY DESIGN and METHODS of DATA COLLECTION AND DATA ANALYSIS

The study will take place at St George's Hospital.

5.1 Methods:

A prospective observational study of patients with confirmed CO exposure. All patients will be fully assessed with a full neurological assessment and examination, a detailed battery of cognitive tests, behavioural questionnaires and blood biomarkers sensitive to persistent neuronal (brain) injury:

- The study will use Cogniclinic, a set of brief computerised cognitive tests that can be undertaken on a tablet computer which have been validated in other forms of acquired brain injuries including traumatic brain injury. This form of cognitive assessment benefits from the fact that it is easy to use and can be used in any setting. The App is free and was developed by researchers at Imperial College, London
(https://quicktech.imperialinnovations.co.uk/i/software_apps/cognitron.html)
- Patients will also complete a full set of validated behavioural questionnaires that assess quality of life, depressive symptoms, anxiety levels, post-traumatic stress symptoms, fatigue, apathy, return to work and a newly developed questionnaire that will aim to identify the presence of common post-CO exposure symptoms.

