- Two 4ml samples will be taken which will be sent to the UK Dementia Research Institute at UCL ([name]'s Group) to test for neurological blood biomarkers. Research blood sample bottles will be labelled with a unique study identifier and processed according to study laboratory procedures. Blood samples will be sent to measure levels of protein biomarkers sensitive to neuronal injury. Neurofilament light (NfL) is a sensitive blood biomarker of persistent brain injury and neuronal loss. Increased levels are observed in a variety of neurodegenerative diseases, including Alzheimer's disease and motor neuron disease. Levels also remain elevated in the chronic phase after a traumatic brain injury in some individuals and relate to evidence of progressive brain atrophy (shrinkage). This may be relevant after CO exposure as some patients have progressive symptoms and it is a possible risk factor for the development of dementia. Blood biomarkers will include NfL, tau and glial fibrillary acidic protein.

Cognitive and blood biomarker assessment after CO Exposure

Once enrolled, participants will be given a unique study identifier that will be used for all data collection, tests and blood samples. All data will be stored on a password-protected database on the Hospital's servers accessible to just members of the research team. Statistical analysis will be conducted using SPSS and R. Data analysis will take place at St George's hospital and with members of the research team based at St George's University of London. The unique study identifier will be linked to the individuals' personal data on a separate password-protected database held on the Hospital's servers.

Cognitive tests and questionnaires will be compared to those from large normative control databases to identify differences between the study group (participants exposed to CO) and healthy controls. Blood tests will also be compared to a database of healthy controls to identify changes in these biomarkers after CO exposure.

The relationship between the blood biomarkers and cognitive tests/behavioural questionnaires will also be analysed to see whether there is a correlation between cognitive/behavioural impairments and evidence of brain cell injury as identified by the blood biomarkers.

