Data collected from the cognitive tests and the questionnaires will be transcribed onto the main study database as soon after completion as possible. All results will be ascribed to the participants study identifier and no personal identifiable data will be included in the results database. Paper copies of the questionnaires will be kept with the participant files in a locked filing cabinet in a locked room. The blood samples will be sent as a batch with only the unique study identifier at the end of the study for analysis. No personal identifiable data will be sent with the blood samples. The results will be returned electronically via a password-protected encrypted database and transcribed to the main study database.

The data will be archived according to the Sponsor's standard operative procedure.

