7.1 Eligibility Criteria

50 individuals with confirmed evidence of CO exposure will be recruited. This will allow assessment of common sequelae after CO exposure.

7.1.1 Inclusion criteria:

- Individuals identified as having confirmed exposure to CO between 2 weeks to 2 years at time of assessment. CO exposure determined by either;
 - documented COHb levels above 1.6% in non-smokers and above 6.3% in smokers.
 - or, individuals with evidence of being exposed to raised levels of CO and symptoms

7.1.2 Exclusion criteria:

- age <18 years
- actual or suspected smoke inhalation
- significant neurological or psychiatric illness prior to CO exposure
- inability to provide consent

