7.2 Sampling

7.2.1 Size of sample

50 participants will be recruited.

The average value for serum neurofilament light (NFL) in a large sample of healthy controls was 22.9pg/ml (IQR 16.8-31.4) (Disanto G, Barro C, Benkert P, et al. Serum neurofilament light: a biomarker of neuronal damage in multiple sclerosis. *Annals of neurology*. 2017 Jun;81(6):857-70).

Using a sample of size of 50 allows an effect size of 0.46 on serum NFL levels to be detected with power 0.9 and type 1 error rate of 5%.

This sample size allows a relatively small change in serum NFL levels to be detected but as we do not know whether all CO exposed patients will have raised levels and we will have a range of levels of exposure, this sample size will allow us to explore these issues.

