7.2.3 Biological Sample Handling

Sample collection

Two samples of 4-5ml each to be collected from each participant:

- Serum (gel tube). One 10 or 7mL tube
- Plasma(EDTA-K2 tube, purple cap). One 10 or 7mL tube

Processing at St George's lab

Tubs will be mixed by turning up and down 8-10 times. The serum sample will be allowed to coagulate for >30 min.

Serum:

After coagulation, it will be centrifuged at 2500 x g for 20 minutes with temperature set at +4°C.

Plasma:

It will be centrifuged at 2500 x g for 20 minutes with temperature set at +4°C.

Aliquotation and storage

0.5-1.0 mL aliquots of the samples will be pipetted into cryotubes.

All tubes will be labelled (patient unique studyID, date etc.) and frozen immediately at -80°C.

Cognitive and blood biomarker assessment after CO Exposure

Samples will be stored at St. George's Hospital until all samples have been collected. Samples will then be sent in bulk by specialist courier to the UK Dementia Research Institute at UCL ([name]'s Group) to test for neurological blood biomarkers. Upon completion of sample analysis, remaining sample material will be disposed in accordance with the Human Tissue Authority's Code of Practice.

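### The primary biomarker contrast sets patient samples, dispatched together at study end, against an unnamed control database, and nothing in the protocol puts the two on one assay scale

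*Protocol*

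**What the plan says.** The primary aim (protocol, section 4.1) is "To determine whether blood biomarkers sensitive to neuronal injury are elevated in the sub-acute to chronic period following confirmed environmental, non-fire related exposure to CO". That question needs a reference level.

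The reference is set in section 5.1: "Blood tests will also be compared to a database of healthy controls to identify changes in these biomarkers after CO exposure". The database is not named, and no laboratory, platform, sample matrix or period is given for it.

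On the patient side, section 7.1 states that "50 individuals with confirmed evidence of CO exposure will be recruited", and no section provides for control participants. Section 7.2.3 collects both serum and EDTA plasma, then says "Samples will be stored at St. George's Hospital until all samples have been collected" and "Samples will then be sent in bulk by specialist courier" to one outside laboratory. Section 5.1 agrees on the timing: "The blood samples will be sent as a batch with only the unique study identifier at the end of the study for analysis".

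The sample-size section (7.2.1) takes its control figure from a published multiple sclerosis study: "The average value for serum neurofilament light (NFL) in a large sample of healthy controls was 22.9pg/ml (IQR 16.8-31.4"). It concludes: "Using a sample of size of 50 allows an effect size of 0.46 on serum NFL levels to be detected", with power 0.9 and a 5% type 1 error rate.

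**The concern.** If the plan is followed as written, the patient values come from assays run after the end-of-study shipment, and the control values come from whatever runs built the database. Exposure status and assay occasion then coincide. A difference in calibration, reagent lot, platform or matrix would look exactly like a difference between exposed and unexposed people. Adjusting for age or other participant characteristics would not remove it, and a larger database would not average it away.

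The conclusion at stake is the primary one. An upward shift could produce an apparent rise in neurofilament light (NfL) where there is none, and a downward shift could hide a real one. Without material common to both sets of runs, the data could not show which had happened. The same applies to tau and glial fibrillary acidic protein, for which the protocol gives no reference value.

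**Working it through.** **Inputs from the protocol (section 7.2.1).** n = 50; standardised effect 0.46; power 0.9; type 1 error 5%, sidedness not stated; control average 22.9 pg/ml; control IQR 16.8 to 31.4 pg/ml.

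**Assumptions, not in the protocol.** Control NfL is log-normal. The assay shift is multiplicative, with sizes from 5% to 20% chosen only to show a range.

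**Step 1: reproduce the stated figure.** For a two-sided one-sample z test against a fixed reference, n = ((1.960 + 1.282)/0.46)² = 49.66, rounded up to 50, with power 0.902 at n = 50. The one-sample t test gives power 0.890. A two-sided comparison of 50 with 50 gives only 0.633. The stated figure is therefore that of a one-sample test, in which the control mean is taken as known without error and no control sample enters.

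**Step 2: put the effect on the assay scale.** The IQR of a normal variable spans 1.349 SD, so the control log-SD is ln(31.4/16.8)/1.349 = 0.464. The geometric midpoint of the IQR is √(16.8 × 31.4) = 22.97, close to the stated 22.9, which fits the log-normal assumption. An effect of 0.46 SD is then exp(0.46 × 0.464) = 1.24, a rise of about 24% (22.9 to about 28.3 pg/ml). At n = 50 the t test first reaches significance at 2.010/√50 = 0.284 SD, an observed rise of exp(0.284 × 0.464) = 1.14, or about 14%.

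**Step 3: upward shift, no true effect.** A shift of x% moves the patient mean by ln(1 + x/100)/0.464 SD. Rejection probability of the two-sided one-sample t test, n = 50:

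| Assumed shift | Shift in SD | Rejection rate |
|---|---|---|
| none | 0 | 5% |
| +5% | 0.11 | 11% |
| +10% | 0.21 | 30% |
| +15% | 0.30 | 55% |
| +20% | 0.39 | 78% |

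**Step 4: downward shift, true effect 0.46 SD.**

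| Assumed shift | Apparent effect in SD | Power |
|---|---|---|
| none | 0.46 | 0.89 |
| −5% | 0.46 − 0.11 = 0.35 | 0.68 |
| −10% | 0.46 − 0.23 = 0.23 | 0.36 |

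**Step 5: does a finite control database change this?** With an assumed 250 controls (z approximation, standard error √(1/50 + 1/250)), upward shifts of 5%, 10% and 20% give rejection rates of 10%, 26% and 72%. The one-sample z values are 12%, 31% and 79%. Counting the controls' sampling error lowers the rates a little, but the bias remains.

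**The case against.** A reader might infer that all patient samples are assayed in one run, that controls are barred from it, or that the database is known to come from a different assay. The protocol supports none of these. Its batch and bulk wording describes dispatch, so several plates may be run. The absence of controls is inferred from silence together with the database sentence. The database is unnamed, so a mismatch is possible but not shown. These limits stand.

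Batching is also not the fault. Storing and shipping together limits drift among patients and helps the planned correlations between biomarkers and cognitive or behavioural scores. Staggered shipment would not repair the control comparison. This stands too: the defect lies in the database sentence.

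Section 5.1 refers sample processing to laboratory procedures that are not at hand, and run quality control usually sits in such documents. That could cover how an assay is run. It does not settle which comparator is admissible or which samples travel with the shipment. Those are design choices, and section 7.2.3 already describes sample handling down to centrifuge settings.

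Finally, this is a convenience sample of 50 in a partly exploratory study, where an external reference is a recognised limitation, and the shift sizes above are assumed. That bears on how serious the point is. The point itself remains, because a better comparison can be had for a few extra assays.

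**Conclusion.** The point holds in a limited form. Only exposed patients are sampled, their samples leave together at study end, and the primary question is answered against an existing control database. The protocol requires neither shared samples nor a common laboratory, platform or matrix. As written, an assay difference and an exposure effect cannot be separated in the patient-versus-control contrast. The patient-only correlations are not affected by this difference.

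The size is illustrative. It rests on log-normality, the stated IQR, a one-sample t test at n = 50 and assumed shifts. Under these, a shift well below the 24% target effect is enough to matter: +10% takes the false-positive rate to about 30%, and −10% takes power to about 0.36. It would be wrong to read this as showing that the result will be biased, since the protocol gives no run-to-run figure and the database may turn out to come from the same laboratory and assay. The change is worth making before the shipment. Section 7.2.3 has leftover material disposed of once analysis is complete, so the comparison may not be recoverable afterwards.

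**What to change.** Amend section 5.1, before any sample is assayed, as follows.

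- Keep the end-of-study batch dispatch.
- Name the control database and take control values only from the same laboratory, platform and matrix as the patient values, stating whether the comparison uses serum or EDTA plasma.
- Include in the patient runs a small blinded set of stored control aliquots already measured for that database, and use them to put both sets of values on one scale. If no aliquots are held, use quality-control material common to both sets of runs. This works only if the same material was run on both occasions and the records survive.
- If neither is available, report the NfL contrast with the external database as unable to distinguish exposure from assay differences.

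The cost is a few extra assays, a possibly smaller set of eligible controls, and a slightly wider interval once calibration uncertainty is carried through. No new participants are needed.

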6 STUDY SETTING

The study will take place at St George's Hospital and is a single centre study.

Patients will have confirmed CO exposure as detailed below and will be assessed in the sub-acute to chronic timeframe (2 weeks to 2 years post exposure). Participants will be considered eligible for enrolment into this study if they fulfil all of the inclusion criteria and none of the exclusion criteria as defined below.

Participants will be identified via a National NHS clinic at St George's Hospital, London that assesses and treats patients with previous CO exposure.

7 SAMPLE AND RECRUITMENT

Cognitive and blood biomarker assessment after CO Exposure

7.1 Eligibility Criteria

50 individuals with confirmed evidence of CO exposure will be recruited. This will allow assessment of common sequelae after CO exposure.

7.1.1 Inclusion criteria:

- Individuals identified as having confirmed exposure to CO between 2 weeks to 2 years at time of assessment. CO exposure determined by either;
 - documented COHb levels above 1.6% in non-smokers and above 6.3% in smokers.
 - or, individuals with evidence of being exposed to raised levels of CO and symptoms

7.1.2 Exclusion criteria:

- age <18 years
- actual or suspected smoke inhalation
- significant neurological or psychiatric illness prior to CO exposure
- inability to provide consent

7.2 Sampling

7.2.1 Size of sample

50 participants will be recruited.

The average value for serum neurofilament light (NFL) in a large sample of healthy controls was 22.9pg/ml (IQR 16.8-31.4) (Disanto G, Barro C, Benkert P, et al. Serum neurofilament light: a biomarker of neuronal damage in multiple sclerosis. *Annals of neurology*. 2017 Jun;81(6):857-70).

Using a sample of size of 50 allows an effect size of 0.46 on serum NFL levels to be detected with power 0.9 and type 1 error rate of 5%.

This sample size allows a relatively small change in serum NFL levels to be detected but as we do not know whether all CO exposed patients will have raised levels and we will have a range of levels of exposure, this sample size will allow us to explore these issues.

7.2.2 Sampling technique

A convenience sampling technique will be employed with participants identified via a National NHS clinic at St George's Hospital, London that assesses and treats patients with previous CO exposure. All participants will have confirmed exposure to CO and individuals with only suspected exposure will not be included. If eligible for participation, patients will be provided with an information leaflet and asked if they would like to participate. Any individual with confirmed CO exposure can be referred into this clinic nationally. It is also linked to an on going study, the EDCO study (IRAS 248936), which is screening individuals for carbon monoxide exposure in emergency departments. Individuals identified as having been exposed to CO from this study will be offered a follow up in this clinic. This sampling technique has been used to optimise recruitment given the fact CO exposure is relatively rare.

Cognitive and blood biomarker assessment after CO Exposure

7.2 Recruitment

Patient recruitment will only commence once evidence of the following approval / essential documents are in place:

1. REC approval
2. Final sponsorship permissions,

Participant Identification

Potential participants will be reviewed in a specialist Neurology outpatient clinic designed to assess and manage patients exposed to CO with neurological problems.

This clinic is linked to a current research study (the EDCO study, a study screening for carbon monoxide exposure in emergency departments). Patients identified as having been exposed to CO will be routinely referred in to this clinic for clinical care. The PI for this study is the clinical lead for this outpatient clinic and will therefore have access to identifiable personal data in order to provide the clinical care and will be able to review the medical records in order to be able to determine suitability.

Any patient nationally with confirmed CO exposure can be referred to this clinic but recruitment to the study will only occur once patients are reviewed in the clinic and participants to the study will not be recruited via other channels. The clinic will be publicised so that other healthcare professionals are aware of it so that patients can be assessed and reviewed clinically.

7.2.1 Consent

The Principal Investigator (PI), or an appropriately trained member of the team will obtain informed consent. Eligible patients will be provided with a written patient information sheet describing the study and the study team will be available to answer any questions. The patient will be given adequate time to read the information and consider their participation in the study. Due to the perceived low risk, burden and minimally invasive nature of the study, consent will be sought during the same routine clinic appointment in which patients are approached about the study by the clinical team. If they wish to take part they will then go through the written consent process.

The patient will be informed that their medical records are subject to review by representatives of the sponsor as necessary and that data will be collected and processed in accordance with the Data Protection Act 2018. The patient will be told that participation in the study is voluntary and that they are free to withdraw from the study at any time and without prejudice. If patients are willing to provide a reason for their withdrawal, this information will be recorded. Each patient will be advised that data collected may be published or presented at scientific meetings and may also be subject to audit procedures from Regulatory Authorities. All such personally identifiable data will be pseudo-anonymised to maintain patient confidentiality.

A copy of the signed Informed Consent Form (ICF) along with a copy of the most recent approved Patient Information Sheet (PIS) will be given to the study participant. The original signed & dated consent form will be placed in the ISF and a copy retained in the medical notes.

Cognitive and blood biomarker assessment after CO Exposure

If new information results in significant changes to the risk–benefit assessment, the consent form will be reviewed and updated if necessary. All participants, including those already being treated, will be informed of the new information, given a copy of the revised consent form and asked to re-consent if they choose to continue in the study.

7.2.2 Data collection tool

Paper Case Report Forms (CRFs) will be used. All data will be entered legibly in black ink with a ball-point pen. If the investigator makes an error, it will be crossed through with a single line in such a way to ensure that the original entry can still be read. The correct entry will then be clearly inserted. The amendment will be initialled and dated by the person making the correction immediately. Overwriting or use of correction fluid will not be permitted.

It is the investigator's responsibility to ensure the accuracy of all data entered and recorded in the CRFs. The *delegation of responsibilities log* will identify all study personnel responsible for data collection, entry, handling and managing the database.

Patients will undergo a full medical history and examination. Data including COHb levels at time of exposure, medical and drug history will initially be entered into the medical notes as part of routine clinical care and if the participant wishes to take part in the study the relevant data will be transcribed onto the paper CRF.

Behavioural questionnaires and cognitive assessment results will be entered into a password-protected spreadsheet/database on the NHS computing network.

